#### **Medical Record Review**

All records reviewed will be from clinical care. All participants will provide HIPAA authorization as part of informed consent to request this information and permit its inclusion in the study. Additional permission for records requests from external health systems may be provided by the participant to the study.

A review of medical records will be performed at baseline for all participants during their active study period. This will include insurance type, comorbidity evaluation, date of first dialysis ever, information from Form 2728 about pre-dialysis care, medications, dialysis schedule. ED visits and hospitalizations.

Monthly medical record review will include dialysis treatment duration prescribed and delivered, interdialytic weight gain mean (%) for the month, serum albumin, ED visits and unplanned hospitalizations.

## **8.2 SAFETY ASSESSMENTS**

There are no dedicated safety assessments in this study given no more than minimal risk related to the intervention. However, all participants have a serious chronic medical condition (ESKD requiring dialysis). Coordinators will be trained to report any unexpected events to study PIs. Planned evaluations include feedback about the intervention to report concerns, or suggestions for improvements.

## **8.3 ADVERSE EVENTS AND SERIOUS ADVERSE EVENTS**

### **8.3.1 DEFINITION OF ADVERSE EVENTS**

Due to the nature of the intervention this study is considered no more than minimal risk to participants. However, monitoring for adverse events will be included as described below given the study population is medically complex and at high risk for health events independent of the study.

This protocol uses the definition of adverse event from 21 CFR 312.32 (a): any untoward occurrence associated with the use of an intervention in humans, ***whether or not considered intervention-related***. Examples may include emotional distress, or study related anxiety.

- The adverse events for mentors associated with this study include:
  - Distress related to curriculum training duration and skills assessments
  - Distress related to telephone conversations with assigned mentees
- The adverse events for patient participants, including intervention mentees, include:
  - The embarrassment and/or stigma of being identified as a high-risk patient
  - Distress related to concern for loss of privacy of health information by mentor disclosure
  - Distress related to telephone conversations with mentors

### 8.3.2 DEFINITION OF SERIOUS ADVERSE EVENTS

A *serious adverse event* (SAE) is any AE that is:

- fatal or results in death
- life-threatening
- requires or prolongs hospital stay
- results in persistent or significant disability or incapacity
- an important medical event\*

\*Important medical events are those that may not be immediately life threatening but are clearly of major clinical significance.

### 8.3.3 CLASSIFICATION OF AN ADVERSE EVENT

#### 8.3.3.1 SEVERITY OF EVENT

All adverse events (AE), including serious adverse events (SAEs) will be assessed by the principal investigator, using the following defined grading system. For any events deemed to be severe, and related to the intervention, a report will be written and submitted to the IRB as well as to the DSMB for further evaluation.

- **Not serious** – Events require minimal or no treatment and do not interfere with the participant's daily activities.
- **Serious** – Events that result in a low level of inconvenience or concern with the therapeutic measures. Moderate events may cause some interference with functioning.
- **Life-threatening** – Events interrupt a participant's usual daily activity and may require treatment. Severe events are usually potentially life-threatening or incapacitating. Of note, the term "severe" does not necessarily equate to "serious".
- **Fatal**

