#### 8.3.5 ADVERSE EVENT REPORTING

All AEs will be assessed by a principal investigator, using the above protocol defined grading system. Disease-related events common in the study population are described in 8.3.3.3. All AEs will be documented on the AE Study Log Form and also in the individual participant research record. If the AE meets the criteria for an SAE it will be documented accordingly and reported to the PIs, DSMB and IRB if indicated (Unexpected and Probably or Definitely related to the Intervention). Events that meet criteria for reporting to the IRB, this will occur within 10 business days and also summarized in the continuing review. If the event is unexpected probably or related to the intervention and results in death, the event will be reported to the IRB within 3 days and also summarized at the continuing review, or as required by the local IRB.

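### Two of the four adverse event severity grades carry labels that do not fit their descriptions, and the *severe* trigger for a written IRB/DSMB report matches no named grade

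*Combined protocol and SAP*

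**What the plan says.** Section 8.3.3.1 sets out four grades under a heading about severity.

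- *Not serious*: little or no treatment needed and no effect on daily activities.
- *Serious*: "Events that result in a low level of inconvenience or concern with the therapeutic measures". The next sentence reads "Moderate events may cause some interference with functioning".
- *Life-threatening*: "Events interrupt a participant's usual daily activity and may require treatment", followed by "Severe events are usually potentially life-threatening or incapacitating". A closing note warns that severe and serious are not necessarily the same thing.
- *Fatal*: no description.

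The section also sets a reporting rule: "For any events deemed to be severe, and related to the intervention, a report will be written and submitted to the IRB", with a copy to the DSMB.

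Section 8.3.2 defines a serious adverse event by outcome: death, threat to life, an event that "requires or prolongs hospital stay", lasting disability or incapacity, or an important medical event.

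Section 8.3.5 makes the scale general: "All AEs will be assessed by a principal investigator, using the above protocol defined grading system". It then gives a separate route for serious adverse events, in which IRB reporting depends on the event being unexpected and probably or definitely related. Section 8.3.6 sends serious adverse events to that route.

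**The concern.** The descriptions read as a mild, moderate and severe intensity scale, but the labels are seriousness and outcome terms. *Serious* therefore has two incompatible meanings in neighbouring sections, and *Life-threatening*, itself a criterion in 8.3.2, is attached to a much broader description.

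Two things are at stake. The first is the recorded grade. Section 8.3.4 puts severity on the adverse event log and tracks changes in it, and 8.3.3.3 uses severity in judging whether an event is expected. The second is the written report in 8.3.3.1. An investigator is told to report severe, related events but not which grade that means.

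**Working it through.** No arithmetic applies. The check sets the labels, descriptions and triggers side by side.

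**Step 1: label against description, with 8.3.2 as the reference.**

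| Grade in 8.3.3.1 | What the description covers | Agreement with 8.3.2 |
|---|---|---|
| *Not serious* | Minimal treatment, no effect on daily life | Consistent: such an event would not ordinarily meet any criterion |
| *Serious* | Low inconvenience; moderate interference with functioning | Conflict: neither is a criterion |
| *Life-threatening* | First sentence: disruption of ordinary activity. Second sentence: potentially life-threatening or incapacitating | Partial conflict: the first sentence is far broader than the label, the second fits it |
| *Fatal* | Label only | Consistent |

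Two of the four grades are mismatched, one clearly and one in part.

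**Step 2: direction of the error.** Take distress after a mentor call that interferes somewhat with functioning. It cannot be *Not serious*, because that grade excludes interference with daily activities. The next grade is *Serious*, although no criterion in 8.3.2 need be met. Now take an event that disrupts a usual day and may need treatment but poses no threat to life. By the first sentence of its description it is *Life-threatening*. Both shifts are upward.

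**Step 3: what *severe* points to.** The word appears in the trigger and in the text under *Life-threatening*, and nowhere as a grade. At least three readings are open: every event in the *Life-threatening* grade; only those that fit that grade's second sentence; or an intensity judgement made apart from the scale. A related event that disrupts daily activity without threatening life needs the report on the first reading, does not on the second unless it is incapacitating, and is undetermined on the third.

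**Step 4: whether another route settles the matter.**

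| Route | Event must be | Relatedness | Must be unexpected? |
|---|---|---|---|
| 8.3.3.1 written report to IRB and DSMB | Severe | Related, category not stated | No |
| 8.3.5 and 8.3.6, IRB criterion | Serious by 8.3.2 | Probably or definitely | Yes |
| 8.4.1 unanticipated problem | Suggestive of greater risk than previously known | Related or possibly related | Yes |

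Section 8.3.3.3 treats some mentor discomfort and some mentor/mentee conflict as expected. If such an event were severe and related, it would fail the expectedness condition in the second and third rows. Of these three routes, only the 8.3.3.1 report could then bring it individually to the IRB, and that is the route whose trigger names no grade.

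**The case against.** The strongest reply is that serious adverse event status does not depend on this scale. Section 8.3.5 applies the 8.3.2 criteria as its own step, 8.3.6 requires the reason for classing an event as serious to be recorded, and 8.3.3.1 itself separates severe from serious. This stands. A reader might infer that moderate distress would be counted as a serious adverse event, but the documents do not support that.

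The reply can be extended. *Severe* is described under *Life-threatening*, so there is a natural mapping. Sections 8.3.5 and 8.4.2 give independent reporting routes with timelines. Section 7.1 sends safety concerns within pairs to the DSMB, and 10.1.6 sends case reports of adverse events to the DSMB and IRB at least every six months. These are real backstops, and they rule out any inference that safety reporting as a whole fails. They do not say which events meet the 8.3.3.1 trigger, and the natural mapping is never stated.

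Three further inferences also go too far. *Not serious* is compatible with 8.3.2, so the mismatch does not extend to three grades. Both demonstrated shifts are upward, and 9.4.4 says only that adverse events will be tabulated descriptively, without mention of this grade, so tables wrong in both directions are not shown. Finally, the log form and manual of procedures are not among the documents, so it cannot be assumed that events already logged are misgraded.

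**Conclusion.** The point holds as an internal inconsistency in a rule that investigators must apply. Two of four grades have labels that do not fit their descriptions, and one report trigger is tied to no named grade. The size is limited: upward drift in recorded severity, plus uncertainty over one written report, chiefly for severe, related events that the protocol treats as expected. The number of participants or events affected cannot be estimated from the documents.

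The conclusion assumes that investigators grade by the text of 8.3.3.1 as it stands. If the log form uses different labels, the practical effect is smaller, though the protocol text still needs correction. The 8.3.2 determination, the primary endpoint analysis and the power calculation are untouched. The correction is worth making because it is specific and cheap, but the trial's main conclusion does not depend on it.

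**What to change.** 1. In 8.3.3.1, relabel the grades so that each label matches its description and none reuses the word *serious*.
2. State which grade or grades the *severe* trigger means, and which relatedness categories from 8.3.3.2 count.
3. Keep seriousness as the separate determination under 8.3.2, recorded in its own field.
4. Reconcile the triggers in 8.3.3.1, 8.3.5 and 8.3.6, saying expressly whether an expected but severe and related event needs the written report.
5. Check the adverse event log. Regrade only entries graded with the mismatched labels, and confirm whether any of them should have had a report.

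The cost is protocol and form wording, plus a check of existing log entries whose extent depends on what the form shows. No endpoint, analysis model or sample size changes.

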#### 8.3.3.2 RELATIONSHIP TO STUDY INTERVENTION/EXPERIMENTAL MANIPULATION

The study site PI, an expert nephrology clinician, will review the events and determine relatedness with the study intervention. If the determination is not clear, the site PI will engage the DSMB to additionally review a de-identified version of the case and determine relatedness to the study intervention.

The PI and/or DSMB will grade the causality of the adverse event to any element of the study using the following categories.

- **Definitely Related** – The AE is known to occur with the study procedures, there is a reasonable possibility that the study procedures caused the AE, or there is a temporal relationship between the study procedures and the event. Reasonable possibility means that there is evidence to suggest a causal relationship between the study procedures and the AE.
- **Probably Related** – There is evidence to suggest a causal relationship, and the influence of other factors is unlikely. The clinical event, occurs within a reasonable time after administration of the study procedures, is unlikely to be attributed to concurrent disease or other drugs.
- **Potentially Related** – There is some evidence to suggest a causal relationship (e.g., the event occurred within a reasonable time after administration of study procedures). However, other factors may have contributed to the event (e.g., the participant's clinical condition, other concomitant events). Although an AE may rate only as "possibly related" soon after discovery, it can be flagged as requiring more information and later be upgraded to "probably related" or "definitely related", as appropriate.
- **Unlikely to be Related** – There is not a reasonable possibility that the study procedures caused the event, there is no temporal relationship between the study procedures and event onset, or an alternate etiology has been established.

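### The causality scale gives Definitely Related for timing alone, which is less evidence than Probably Related needs, and an event with an established other cause can meet both the top and the bottom grade

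*Combined protocol and SAP*

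**What the plan says.** Section 8.3.3.2 has the site PI, an expert nephrology clinician, judge relatedness. Unclear cases go to the DSMB in de-identified form. There are four grades.

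- **Definitely Related.** The list has three alternatives. The first is that the event is a recognised consequence of what the study does. The other two are: "there is a reasonable possibility that the study procedures caused the AE, or there is a temporal relationship between the study procedures and the event". The last has no time window and no further condition. The section glosses the second as evidence that points to causation.
- **Probably Related.** This grade joins two requirements: "There is evidence to suggest a causal relationship, and the influence of other factors is unlikely". The timing must also be reasonable, and concurrent disease or other drugs an unlikely explanation.
- **Potentially Related.** Here timing appears as an example: "There is some evidence to suggest a causal relationship (e.g., the event occurred within a reasonable time after administration of study procedures". This grade also allows that something else played a part.
- **Unlikely to be Related.** Causation is not reasonably possible, or "there is no temporal relationship between the study procedures and event onset, or an alternate etiology has been established".

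The section treats the scale as ordered, since an event in the third grade may later be raised to one of the top two. It names that grade Potentially Related but calls it possibly related in the text.

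The grade is used in three places. Section 8.3.4 has it recorded in the adverse event log. Section 8.3.3.1 requires a report to the IRB and DSMB for events that are severe and related to the intervention. Section 8.3.5 ties serious event reporting to events that are "Unexpected and Probably or Definitely related to the Intervention", with a three-day IRB report for qualifying deaths.

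**The concern.** The top grade reads like a broad definition of 'related' as opposed to 'not related', placed at the head of a four-level scale. Because its conditions are alternatives, it is the easiest of the related grades to satisfy, not the hardest. The bottom grade is built the same way, so the two ends overlap.

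Two site PIs who both follow the text could give the same event opposite grades. The error can run in either direction. A background dialysis event that happens during the mentoring months can be graded Definitely Related. An event with real evidence of a link to the intervention can be graded Unlikely to be Related because another cause is also on record, and so fall outside the reporting rules. Section 6.3 says that the research team is not blinded, so whoever chooses between the two grades may know the arm.

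**Working it through.** There is no figure in the plan to reproduce. The check is to read the definitions as conditions and see which grades each kind of event meets.

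**Step 1. The conditions.** Let K = known to occur with the study procedures; R = reasonable possibility, which the section explains as evidence suggesting causation; T = temporal relationship; A = alternate etiology established. On the literal wording:

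- Definitely = K or R or T
- Probably = R, and other factors unlikely, and reasonable timing
- Potentially = some causal evidence, of which reasonable timing is the example given
- Unlikely = not R, or not T, or A

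**Step 2. Typical events.**

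| Evidence present | Definitely | Probably | Potentially | Unlikely |
|---|---|---|---|---|
| Timing only (T, not R) | met, by T | not met | met if the timing is reasonable | met, by not R |
| Timing and an established other cause (T, A) | met, by T | not met | arguable | met, by A |
| Causal evidence and timing, but other factors plausible (R, T, not A) | met, by R or T | not met | met | not met |
| Causal evidence, other factors unlikely, reasonable timing (R, T, not A) | met, by R or T | met | first sentence met | not met |

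The first row shows timing alone reaching the top grade and failing the second. In the second row, one event meets both ends of the scale; an access infection with a proven other source that begins during mentoring is an example. The last row shows that every event meeting Probably also meets Definitely, because Probably already requires R. The text therefore gives no rule for stopping at Probably.

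**Step 3. All combinations.** Four yes/no conditions give 2 × 2 × 2 × 2 = 16.

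- Definitely fails only when K, R and T are all absent, with A either way: 2 combinations. So 16 − 2 = 14 meet it.
- Unlikely fails only when R and T are present and A is absent, with K either way: 2 combinations. So 16 − 2 = 14 meet it.
- No combination fails both, so 16 − 2 − 2 = 12 meet both.

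Only 2 of 16 are Definitely without also being Unlikely. Some combinations are clinically implausible, so this count describes the wording and does not estimate how many events are misgraded.

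**Step 4. Is it resolved elsewhere?** Section 8.3.3.3 defines expectedness, not relatedness. Section 8.4.1 has its own definition of possibly related, but for unanticipated problems only. Neither changes the four grades or says which takes precedence when two apply.

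**The case against.** The strongest case on the other side is that little depends on the grade, and much of that case stands.

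- Section 8.3.5 also requires the event to be unexpected. Section 8.3.3.3 lists death, heart failure, coronary events, arrhythmia, access events and infections among those anticipated, so many background dialysis events do not trigger that rule whatever their grade. However, the rule for severe related events in Section 8.3.3.1 has no such condition.
- Section 10.1.6 sends case reports about any adverse events to the DSMB and IRB at least every six months, with no relatedness filter.
- Unclear cases can go to the DSMB. This helps, but the DSMB would use the same definitions, and two PIs can each think a case clear and disagree.

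Four stronger readings are tempting, and the documents do not support them.

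- *The top grade needs strictly less than Potentially Related.* Read literally, it asks for neither causal evidence nor a reasonable interval. But Potentially Related itself offers timing as its example of evidence, so the safe statement is that the top grade needs no more.
- *The grade alone decides reporting.* Severity or unexpectedness is also required, as above.
- *Every admission during mentoring becomes Definitely Related.* The rate in Section 9.2 gives 0.27 × 3 months × 100 mentees = 81 encounters, or 0.27 × 0.80 × 3 × 73 ≈ 47 with 73 mentees and the full 20% reduction. This is an assumption about exposure only. Section 8.3.4 collects these encounters as solicited outcome events and does not establish that each is graded for causality. Temporal relationship is undefined, so treating any event during the mentoring period as temporally related is one reading.
- *The safety results cannot separate harm from background illness.* Section 9.4.4 promises a descriptive tabulation and does not state a table by relatedness. The trial is randomized 1:1, and a comparison of event rates by arm does not depend on individual causality grades.

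**Conclusion.** The point holds as a defect of a stated rule. Followed as written, the scale contradicts its own order: timing alone earns the top grade, less than the second grade needs and no more than the third. The highest and lowest grades also overlap in 12 of 16 literal combinations. This rests on reading the listed conditions as alternatives, which is what the 'or' says. The example of an event during mentoring further assumes that falling within the mentoring period counts as a temporal relationship.

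The consequence is an unreliable relatedness entry in the log and possible misdirection, either way, of reports on severe related events and on unexpected serious events graded Probably or Definitely Related. Nothing in the documents shows that any event has been misgraded. The primary endpoint, its analysis and the power are unaffected. The change should be made because it is cheap and bears on safety reporting, but the trial's main inference does not depend on it.

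**What to change.** Amend Section 8.3.3.2 so that the four grades are ordered and mutually exclusive:

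- Remove temporal relationship and reasonable possibility as sufficient conditions for Definitely Related. Require there at least the causal evidence and the exclusion of other causes that Probably Related requires.
- Place evidence that consists of timing only no higher than Potentially Related.
- State how an established alternate etiology ranks against timing, so that one event cannot meet both ends.
- Use one label for the third grade, either Potentially or possibly.

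The exact wording is open, as several workable scales would meet these requirements. Then check the relatedness grades already in the log against the revised definitions, keeping the existing grade visible beside any change, with the reason.

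The cost is a small protocol amendment with IRB approval and a log check. Section 8.3.4 already has the description, onset and relatedness of each event recorded, so little or no new data should be needed. The check would be done by staff who are not blinded to arm, which is a reason to document each change.
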